2.3.6 Pregnancy test results

Any pregnancies reported will be listed.

2.3.7 Liver toxicity function and liver events

2.3.7.1 Liver toxicity function

The liver toxicity (LFT abnormality) will be identified with the SMQ ‘Drug related hepatic disorders – comprehensive search’ (Broad) and the laboratory parameters mainly AST (aspartate aminotransferase; also known as SGOT), ALT (alanine aminotransferase; also known as SGPT), ALP (alkaline phosphatase) and TBL (total bilirubin; conjugated (direct) and unconjugated (indirect) bilirubin).

The standard SMQ-PT table and odds ratio will be used to provide the number and percentage of subjects with hepatic disorders as mentioned in [Section 2.3.1](#) (hepatotoxicity, SMQ ‘Drug related hepatic disorders – comprehensive search’)

The liver function related parameters will be shown in the laboratory standard tables (see [Section 2.3.2](#)).

In addition, summary tables will be provided on the number and percentage of subjects having the following criteria:

Table 2-8 Criteria for evaluating liver toxicity

Parameter	Criterion
ALT or AST	ALT or AST > 3xULN
	ALT or AST > 5xULN
	ALT or AST > 8xULN
	ALT or AST > 10xULN

Parameter	Criterion
ALT/AST & TBL	ALT or AST >3x ULN and TBL >1.5x ULN ALT or AST >3x ULN and TBL >2x ULN ALT or AST >5x ULN and TBL >2x ULN ALT or AST >8x ULN and TBL >2x ULN ALT or AST >10x ULN and TBL >2x ULN ALT or AST >3x ULN and TBL >2x ULN and ALP <2x ULN
TBL & ALP	TBL >1.5x ULN and ALP >2x ULN TBL >2x ULN and ALP >2x ULN
Isolated TBL	TBL >1.5x ULN & ALT and AST <=3x ULN and ALP <=2x ULN TBL >2x ULN & ALT and AST <=3x ULN and ALP <=2x ULN TBL >3x ULN & ALT and AST <=3x ULN and ALP <=2x ULN
Isolated ALP	ALP >1.5x ULN & ALT and AST <=3x ULN and TBL <=1.5x ULN ALP >2x ULN & ALT and AST <=3x ULN and TBL <=1.5x ULN ALP >3x ULN & ALT and AST <=3x ULN and TBL <=1.5x ULN ALP >5x ULN & ALT and AST <=3x ULN and TBL <=1.5x ULN

ALP: alkaline phosphatase; ALT: alanine aminotransferase; AST: aspartate aminotransferase; TBL: total bilirubin; ULN: upper limit of normal.

Plots showing the relationship between TBL and ALT or AST (eDish plot) will also be provided.

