## 4.2 Exclusion criteria

Patients fulfilling **any** of the following criteria are not eligible for inclusion in this study. No additional exclusions may be applied by the investigator, in order to ensure that the study population will be representative of all eligible patients.

1. Dyspnea due to non-cardiac causes, such as acute or chronic respiratory disorders or infections (i.e., severe chronic obstructive pulmonary disease, bronchitis, pneumonia), which may interfere with the ability to interpret the primary cause of dyspnea.
2. Known history of respiratory disorders requiring the daily use of IV or oral steroids (does not include inhaled steroids); need for intubation or the current use of IV or oral steroids for COPD.
3. Patients with blood pressure > 180 mmHg at the time of randomization or persistent heart rate > 130 bpm.
4. Temperature >38.5°C (oral or equivalent) or sepsis or active infection requiring IV anti-microbial treatment
5. Clinical evidence of acute coronary syndrome currently or within 30 days prior to enrollment. (Note: the diagnosis of acute coronary syndrome is a clinical diagnosis and that the sole presence of elevated troponin concentrations is not sufficient for a diagnosis of acute coronary syndrome, given that troponin concentrations may be significantly increased in the setting of AHF.)
6. AHF due to significant arrhythmias, which include any of the following: sustained ventricular tachycardia, bradycardia with sustained ventricular rate <45 beats per minute, or atrial fibrillation/flutter with sustained ventricular response of >130 beats per minute
7. Patients with severe renal impairment defined as pre-randomization eGFR < 25 mL/min/1.73m^2 calculated using the sMDRD equation, and/or those receiving current or planned dialysis or ultrafiltration
8. Patients with hematocrit <25%, or a history of blood transfusion within the 14 days prior to screening, or active life-threatening GI bleeding.
9. Known hepatic impairment (as evidenced by total bilirubin > 3 mg/dL, or increased ammonia levels, if performed) or history of cirrhosis with evidence of portal hypertension such as varices.
10. Significant, uncorrected, left ventricular outflow obstruction, such as obstructive hypertrophic cardiomyopathy or severe aortic stenosis (i.e., aortic valve area <1.0 cm^2 or mean gradient >40 mmHg on prior or current echocardiogram), and severe mitral stenosis

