### 7.3 Liver safety monitoring

#### Hepatotoxicity clinical safety standard guideline

Hepatic dysfunction as sequelae of HF, even with modest cardiac compromise, has long been recognized. Passive hepatic congestion due to increased central venous pressure and low hepatic perfusion, reflecting impaired hemodynamics due to decreased cardiac output and profound hypotension, are considered causative mechanisms. Subsequent atrophy of liver cells and edema of the peripheral hepatic parenchyma are both leading to hepatocellular hypoxia; additionally PaO2 alterations can add to the hepatic injury. These events present both acutely with cardiac decompensation events and chronically with low-grade hepatic compromise resulting in fibrosis or cirrhosis ([Alvarez and Mukherjee 2011](#); [Nikolau et al 2013](#)).

Since cardiac induced hepatic injury can mask hepatotoxic events, it is important to clearly determine the underlying cause of elevations of liver function tests (LFTs) that may occur during the course of this study. Therefore, to ensure patient safety and enhance reliability in determining the hepatotoxic potential of an investigational drug, a standardized process for identification, monitoring and evaluation of liver events has to be followed.

Liver events, **which cannot be solely explained by apparent cardiac decompensation as the underlying cause (i.e., another etiology is suspected to cause or contribute to this event)**, are divided into two categories:

- Liver laboratory triggers, which will require repeated assessments of the abnormal laboratory parameter
- Liver events, which will require close observation, follow-up monitoring and completion of the standard base liver CRF pages

Please refer to [Table 15-1 in Appendix 2](#) for complete definitions of liver laboratory triggers and liver events.

Every liver laboratory trigger of liver event **without apparent cardiac decompensation as the underlying cause** and as defined in [Table 15-1 of Appendix 2](#) should be followed up by the investigator or designated personal at the trial site as summarized below. Detailed information is outlined in [Table 15-2 in Appendix 2](#).

For the liver laboratory trigger:

- Repeating the LFT within the next week to confirm elevation.

Repeat laboratory tests should be entered on the appropriate unscheduled local laboratory CRF page.

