2.3.2 Laboratory data

2.3.2.1 Hematology and chemistry

In addition to local laboratory evaluations for all randomized subject, a laboratory substudy will be conducted at a subset of selected sites to enroll at least 1600 subjects. Subjects without written informed consent for the laboratory substudy before any study-specific assessment is performed will be excluded from the population.

Descriptive summaries of actual and change from baseline will be presented for all continuous clinical laboratory values by treatment and time point.

Clinical shift tables showing the pattern of change from baseline versus each post-baseline time point will be presented based on the cross-classification of the number of subjects with clinical laboratory values below (low), within (normal), or above (high) normal ranges for each laboratory test.

All laboratory data will be listed for each subject. Laboratory values that are outside the normal ranges will be flagged high (H) or low (L).

The number and percentage of subjects with clinically notable laboratory results, including categorical analysis on laboratory parameters of interest after baseline will be presented. Clinically notable laboratory values are defined in protocol Appendix 1. The notable laboratory values related to liver function are detailed in [Section 2.3.7](#).

The data from local and central laboratory will be presented separately.

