2.3.4 Electrocardiogram (ECG)

An ECG substudy will be conducted at a subset of selected sites to enroll at least 500 subjects. Subjects without written informed consent for the ECG substudy before any study-specific assessment is performed will be excluded from the population.

The analyses will be performed based on subjects who have at least one ECG at baseline (ECG recordings taken before the infusion starts will be considered) and one ECG post baseline (48 hour time point) which is recorded within 60 minutes after study drug infusion ends.

The following quantitative variables will be summarized: RR interval, PR interval, QRS duration, QT interval, and corrected QT interval (QTc).

The number and percentage of subjects with the following criterion will be presented.

- QT > 500 msec
- QT > 480 msec
- QT > 450 msec
- QT > 450 msec, male only
- QT > 460 msec, female only
- QT increases from baseline > 30 msec
- QT increases from baseline > 60 msec
- PR > 200
- PR > 220 msec
- PR increases from baseline > 25%
- QRS > 110 msec and increase from baseline $\geq 25\%$
- QRS > 120 msec and increase from baseline $\geq 25\%$
- Heart rate > 100 beats per minute and increase from baseline $\geq 25\%$
- Heart rate < 50 beats per minute and decrease from baseline $\geq 25\%$

QT data will be analyzed for both the Fridericia (primary) and Bazett's (secondary) corrections.

Newly occurring abnormalities in ECG morphology will be summarized by treatment group and overall. Newly occurring is defined as no occurrence on any of the baseline ECGs with the presence of the finding on any single ECG post baseline.

A listing of all abnormalities will be provided, as well as a by-subject listing of all quantitative ECG parameters.

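### SAP Table 2-8 does not separate liver abnormalities already present at baseline from new ones, so persisting congestive cases dilute the relative contrast between arms

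*SAP*

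**What the plan says.** SAP 2.3.7.1 states that "summary tables will be provided on the number and percentage of subjects having the following criteria". Table 2-8 then gives rows for ALT or AST, for ALT/AST combined with total bilirubin (TBL), for TBL with ALP, and for isolated TBL and isolated ALP, all as multiples of ULN. The section names no time window, has no rule for newly occurring cases and does not split by baseline status. It also plans a plot of TBL against ALT or AST (eDish).

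The time window has to be taken from SAP 2.3.2.1. There the count of clinically notable results, "including categorical analysis on laboratory parameters of interest after baseline will be presented", and "The notable laboratory values related to liver function are detailed in" Section 2.3.7. The SAP document history also calls Table 2-8 a categorical analysis of liver function. The sensible reading is therefore that Table 2-8 uses post-baseline values.

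Other displays in SAP 2.3.2.1 do use baseline: "Descriptive summaries of actual and change from baseline will be presented for all continuous clinical laboratory values by treatment and time point", and "Clinical shift tables showing the pattern of change from baseline versus each post-baseline time point will be presented". Those shift tables classify values as low, normal or high.

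On the population, Protocol 7.3 says: "Since cardiac induced hepatic injury can mask hepatotoxic events, it is important to clearly determine the underlying cause of elevations". Protocol 4.2, exclusion 9, reads in part "Known hepatic impairment (as evidenced by total bilirubin > 3 mg/dL, or increased ammonia levels, if performed"; it also covers cirrhosis with portal hypertension. No ALT, AST or ALP limit is set.

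**The concern.** Patients enter during acute decompensation, when congestion can itself raise liver tests. Liver chemistry is then measured daily in hospital. Someone who meets a Table 2-8 criterion before study drug and still meets it the next day enters the same count as someone who first meets it on drug.

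Bilirubin shows that this can happen under the entry rules. The documents give no ULN in mg/dL. If it is assumed to be 1.0 to 1.2, the 3 mg/dL limit is 3/1.2 = 2.5 to 3/1.0 = 3.0 times ULN. An eligible patient with ALT and AST no higher than 3 times ULN and ALP no higher than 2 times ULN could thus already meet the isolated-TBL row above 2 times ULN. On this range such a patient cannot meet the isolated row above 3 times ULN. The ALT/AST and ALP rows, and the combined rows, have no entry limit on the enzymes at all.

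At stake is how readable the table is. It is the planned tabulation by ULN multiples and by combined ALT/AST-and-TBL pattern, including the potential Hy's Law pattern. Background cases that predate treatment weaken the ratio between arms and widen the uncertainty around the difference.

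**Working it through.** **Inputs.** Planned size is 6,800 randomized 1:1 (Protocol 3.1), so about 3,400 per arm, taken as the approximate safety-set size. The documents state no liver rate, so there is no figure of the plan's own to reproduce. The following are assumptions:
- b, the share meeting a criterion at baseline: 3%, 5% or 10%
- q, the share of those still meeting it at a later sample: 90%
- r, new onset among the rest: 1% on placebo and 2% on serelaxin

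**Formulas.** Proportion counted in one arm = b·q + (1 − b)·r. Risk difference = (1 − b)(r_S − r_P) + b(q_S − q_P), with S for serelaxin and P for placebo.

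**Equal persistence, worked at b = 5%.**
- Placebo: 0.05 × 0.9 + 0.95 × 0.01 = 5.45%
- Serelaxin: 0.05 × 0.9 + 0.95 × 0.02 = 6.40%
- Ratio 6.40/5.45 = 1.17; difference 0.95 points

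The same formula gives:

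| b | Placebo | Serelaxin | Ratio | Difference (points) |
|---|---|---|---|---|
| 3% | 3.67% | 4.64% | 1.26 | 0.97 |
| 5% | 5.45% | 6.40% | 1.17 | 0.95 |
| 10% | 9.90% | 10.80% | 1.09 | 0.90 |

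Counting only newly occurring cases gives 1% versus 2% throughout: ratio 2.0, difference 1.00 point.

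**Precision at b = 5%.**
- All cases counted: standard error of the difference = √[(0.0545 × 0.9455 + 0.0640 × 0.9360)/3,400] = 0.57 points. The 95% interval is 0.95 ± 1.96 × 0.57, about −0.2 to 2.1.
- New cases only, 3,400 × 0.95 = 3,230 per arm: √[(0.01 × 0.99 + 0.02 × 0.98)/3,230] = 0.30 points. The 95% interval is 1.00 ± 1.96 × 0.30, about 0.4 to 1.6.

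**Range over other assumptions.** With new onset 1% versus 2% and b from 2% to 20%, the ratio runs from 1.33 to 1.04 if every baseline case persists, and from 1.49 to 1.07 if half do. The difference runs from 0.98 to 0.80 points. At b = 5% with full persistence, onset of 0.5% versus 1% gives a ratio of 1.09 instead of 2.00, and 2% versus 3% gives 1.14 instead of 1.50.

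**Unequal persistence.** If 80% persist on serelaxin and 90% on placebo, the difference becomes:
- b = 3%: 0.97 − 0.03 × 10 = 0.67 points
- b = 5%: 0.95 − 0.05 × 10 = 0.45 points
- b = 10%: 0.90 − 0.10 × 10 = −0.10 points

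Randomization balances b in expectation, but persistence is a post-treatment quantity and is not balanced by it.

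**Can the planned displays recover the split?** A patient going from 1.5 to 8 times ULN is high at both times in a low/normal/high shift table. That table also handles one test at a time, so it cannot reproduce the combined rows. Mean changes from baseline do not show rare individual cases.

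**The case against.** The strongest reply has four parts.

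1. The SAP is silent; it does not state that baseline cases are counted. Read with SAP 2.3.2.1, a value present only at baseline drops out. This stands, and the point is limited to abnormalities that persist or recur.
2. Table 2-8 reports only numbers and percentages. The odds ratio mentioned in SAP 2.3.7.1 belongs to the adverse-event grouping for hepatic disorders. On the planned percentages, the absolute excess at 5% prevalence is still 0.95 points, about 32 patients per 3,400. This also stands, given equal persistence.
3. Baseline and cause are handled elsewhere. Protocol 10.5.2 counts adverse events as incident only if they begin after study drug starts, and plans shift tables with extended normal ranges to the most extreme value. SAP 2.3.7.2 lists reported liver events with relationship to drug and alternative diagnoses, and Protocol 7.3 requires a causality assessment for liver events. This largely stands, with limits: under Protocol 7.1 a laboratory abnormality is an adverse event only if symptomatic, clinically significant or treated, and liver-event pages are listed, not compared.
4. A newly-occurring rule does not separate drug from cardiac causes, because a fresh decompensation after baseline still counts. That is correct. The rule removes only what was there before treatment.

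The ECG section offers limited support. SAP 2.3.4 says "Newly occurring is defined as no occurrence on any of the baseline ECGs", but only for morphology; its absolute QT and PR thresholds carry no baseline exclusion either.

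**Conclusion.** The point holds in a limited form. Table 2-8 neither excludes nor separates patients who met a criterion at baseline, so persisting congestive abnormality is pooled with new cases. In the central illustration this takes the ratio from 2.0 to about 1.17 and nearly doubles the standard error of the difference (0.57 against 0.30 points), while the difference itself moves only from 1.00 to 0.95 points. Every rate here is assumed, so the true size cannot be found from the documents.

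Two stronger readings are tempting. A reader might infer that a hepatotoxic signal would be hidden. The documents do not support that for the plan as a whole, since change from baseline, shift tables, incident adverse events and liver-event listings remain. A reader might also infer a directional bias in favour of serelaxin. That needs congestive abnormalities to clear faster on serelaxin. Protocol 3.3 and 3.6 report better decongestion in the earlier trial, but no passage gives an effect on the resolution of liver tests. It is a possibility that a split by baseline status would expose, not a finding.

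**What to change.** In SAP 2.3.7.1:
- Define each Table 2-8 row as the criterion met at any post-baseline sample among patients who did not meet it at baseline, with those patients as the denominator. Use the screening value if baseline is missing, as SAP 2.1.3 already provides.
- On separate lines, show patients who met the criterion at baseline and, among them, those who worsened to a higher multiple.
- Mark baseline status on the eDish plot.
- Apply this separately to local and central laboratory data, as SAP 2.3.2.1 already presents them.

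The cost is SAP wording and table programming. Protocol 6.5.4.2 has AST, ALT, ALP and total bilirubin measured locally at screening and daily in hospital, so no new data are needed.

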2.3.7.2 Liver events

Detailed information of liver event is collected only if subjects report liver event.

The following eCRF pages will be collected and details are listed for the reported liver event.

- Medical history possibly contributing to liver dysfunction.
- Liver event overview: details of clinical signs and symptoms, event related to study drug, other alternative diagnoses etc.
- History of alcohol use
- Drugs of abuse history
- Imaging
- Pathology
- Autoimmune
- Viral serology
- Local laboratory liver function test
- Concomitant medication Acetaminophen/Paracetamol

2.4 Interim analyses

It is planned to establish an external and Independent Data Monitoring Committee (DMC) to monitor subject safety data on a regular basis during the course of the study. For this study, it is planned that the DMC will review safety data on a regular frequency, e.g., every six months. DMC may request additional safety data review. Such safety analyses do not inflate the type I error for the primary efficacy hypothesis testing and thus require no multiplicity adjustments.

It is planned to have one formal interim efficacy analyses. The cut-off for this interim analysis is planned when the information fraction (number of confirmed CV deaths relative to the targeted total number of confirmed CV death at the study completion) of 60% is achieved (corresponding to 329 CV deaths). Some adjustment to the time of interim analysis may be made to coincide with the regular DMC meetings. One-sided tests will be performed and appropriate statistical adjustments for the interim analysis actually performed will be made to ensure the overall one-sided type I error of 0.02 (Lan-DeMets spending function to match an O'Brien-Fleming stopping boundary). For the interim analysis, the analysis dataset will comprise all subjects who were randomized before the cut-off date.

The trial may be concluded early for efficacy, if a significant difference between two treatment arms for the number of CV deaths is achieved by crossing the pre-specified boundary at interim analysis. Interim analysis will be performed by an external independent statistician at an external data analysis center, who will not be involved in the study conduct. The results will be reviewed by the independent DMC. Investigators and others who are involved in the conduct of the trial and in the analysis of the final trial results, or who have contact with study centers, will remain blinded to the treatment codes and interim analysis results until all monitoring decisions have been made and the database has been locked for final analysis.

If the DMC recommends stopping the study due to overwhelming efficacy of CV deaths, i.e., crossing the pre-specified boundary and favorable risk and benefit ratio, the multiple testing procedure in [Figure 2-1](#) will be applied and updated as [Figure 2-2](#) below. The significance levels for WHF, LOS and CVDR are 0.6α , 0.2α and 0.2α .

[figure not shown]
The Lan-DeMets spending function of the O'Brien-Fleming stopping boundary will then be applied to determine the nominal significance level at the interim analysis based on the one-sided alpha of 0.025.

The information fraction at the interim analysis for the three efficacy variables will be calculated as follows:

- WHF: number of randomized subjects at the interim analysis divided by 6800
It is expected that all randomized subjects will have complete WHF information through Day 5, as all patients will be followed up at least 14 days.
- LOS and CVDR: number of randomized subjects at the interim analysis divided by 6800 times 0.9

This assumes that 10% of the efficacy data will be missing at the interim analysis cutoff date.

Figure 2-2 **Sequentially rejective multiple testing procedure if DMC recommends stopping of the study due to overwhelming efficacy in CV death**

Applying the Lan-DeMets spending function of the O’Brien-Fleming stopping boundary if the DMC recommends stopping the study, assuming 70% of the randomized subjects are accrued at the interim analysis, the nominal one-sided alpha for the three efficacy variables are calculated as shown in the Table 2-9.

Table 2-9 **Nominal one-sided alpha at 70% randomized subjects accrued if CVD is rejected**

Efficacy variable	Updated alpha if CVD rejected	Information fraction	Nominal 1-sided alpha at interim analysis
WHF	$0.6 \times 0.025 = 0.015$	0.7	0.0036
LOS	$0.2 \times 0.025 = 0.005$	$0.7 \times 0.9 = 0.63$	0.0004
CVDR	$0.2 \times 0.025 = 0.005$	$0.7 \times 0.9 = 0.63$	0.0004

Note if the boundary is crossed for any of the remaining hypotheses, the multiple testing procedure will reject the hypothesis and update the graph. The nominal one-sided significance level will be re-calculated. The process continues until no hypothesis can be rejected.

For subjects not discharged by interim analysis cutoff date, the LOS will be imputed as the maximum of

- (1) mean value for subjects with actual LOS, including censoring at Day 60 and die in hospital
- (2) LOS at the cutoff date

All cause death will be tested at alpha of 0.025 (one-sided).

